### Protocol

### **Brief Summary:**

This trial is taking place in Los Angeles, CA among patients from primary care practices within the UCLA Health System.

Despite the Advisory Committee on Immunization Practices (ACIP) recommendation in 2010 that all people above 6 months of age should receive an annual flu vaccine, vaccination rates remain low. The investigators plan to assess the effectiveness of reminder/recall messages (direct appointment scheduling, no direct-appointment scheduling, pre-appointment, and no pre-appointment) encouraging influenza vaccinations sent to patient portal users, as well as the effectiveness of a pre-commitment prompt (pre-commitment prompt, no prompt) asking about a patient's intention to get the influenza vaccination, using a 2 x 2 x 2 nested factorial design.

### **Methods and Procedures**

We propose a two-arm randomized controlled trial, and a 2 x 2 x 2 nested factorial design within the treatment arm. Patients are randomized within UCLA primary care practices to intervention arms sent via the portal or a control group. Study arms: 1) standard of care control (no reminder messages, no pre-commitment prompt, except for UCLA employees sent a reminder), 2) direct appointment scheduling reminder, pre-appointment reminder, pre-commitment prompt, 3) direct appointment scheduling reminder, pre-appointment reminder, no pre-commitment prompt, 4) direct appointment scheduling reminder, no pre-appointment reminder, no pre-appointment reminder, no pre-appointment prompt, 5) direct appointment scheduling reminder, no pre-appointment reminder, no pre-commitment prompt 6) No direct appointment scheduling reminder, pre-appointment scheduling reminder, no pre-appointment reminder, pre-appointment reminder, no pre-commitment prompt, 7) No direct appointment scheduling reminder, pre-appointment scheduling reminder, no pre-commitment prompt, 8) No direct appointment scheduling reminder, no pre-commitment prompt, 9) No direct appointment scheduling reminder, no pre-commitment prompt, 9) No direct appointment scheduling reminder, no pre-commitment prompt, 9) No direct appointment scheduling reminder, no pre-commitment prompt, 9) No direct appointment scheduling reminder, no pre-commitment prompt, 9) No direct appointment scheduling reminder, no pre-commitment reminder, no pre-commitment prompt, 9) No direct appointment scheduling reminder, no pre-commitment reminder, no pre-commitment reminder, no pre-commitment prompt, 9)

Study Arm	Intervention/Treatment
No Intervention: Standard of care control	NA
No direct-scheduling or pre-appointment	
portal reminders + No pre-commitment	
prompt	
Participants do not receive any	
reminder/recall messages regarding influenza	
vaccination via the patient portal and do not	
receive a pre-commitment prompt asking if	
they plan to receive the influenza vaccine in	
the upcoming season	

Experimental: Direct appointment scheduling reminder + Pre-appointment reminder + Pre- commitment prompt Participants receive 1) reminder/recall messages regarding influenza vaccination via the patient portal with a link enabling direct scheduling, 2) a pre-appointment reminder that mention asking the provider for a flu vaccine, and 3) a pre-commitment prompt asking if they plan to receive the influenza vaccine in the upcoming season.	
 
Behavioral: Portal Reminders for Influenza
 
Vaccination: Direct scheduling link: Patients
 
receive reminder/recall messages via the
 
patient portal to get an influenza vaccination
 
that include a direct scheduling link, enabling
 
the patient to directly schedule a flu vaccination
 
only visit.
 
Behavioral: Pre-Appointment influenza
 
vaccination reminder: Patients receive modified
 
pre-appointment reminders for upcoming
 
scheduled appointments that include language
 
encouraging patients to ask the provider for the
 
flu vaccine.
 
Behavioral: Pre-commitment prompt
 
Patients receive a pre-commitment prompt
 
asking about their intention to get an influenza
 
vaccination.
 

Experimental: Direct appointment scheduling reminder + Pre-appointment reminder + No pre-commitment prompt Participants 1) reminder/recall messages regarding influenza vaccination via the patient portal with a link enabling direct	Behavioral: Portal Reminders for Influenza Vaccination: Direct scheduling link: Patients receive reminder/recall messages via the patient portal to get an influenza vaccination that include a direct scheduling link, enabling the patient to directly schedule a flu vaccination only visit.
scheduling, and 2) a pre-appointment reminder that mention asking the provider for a flu vaccine, but do not receive a pre- commitment prompt asking if they plan to receive the influenza vaccine in the upcoming season.	Behavioral: Pre-Appointment influenza vaccination reminder: Patients receive modified pre-appointment reminders for upcoming scheduled appointments that include language encouraging patients to ask the provider for the flu vaccine.
Experimental: Direct appointment scheduling reminder + No pre-appointment reminder + Pre-commitment prompt Participants receive 1) reminder/recall messages regarding influenza vaccination via the patient portal with a link enabling direct	Behavioral: Portal Reminders for Influenza Vaccination: Direct scheduling link: Patients receive reminder/recall messages via the patient portal to get an influenza vaccination that include a direct scheduling link, enabling the patient to directly schedule a flu vaccination only visit.
scheduling, and 2) a pre-commitment prompt asking if they plan to receive the influenza vaccine in the upcoming season, but do not	Behavioral: Pre-commitment prompt

receive a pre-appointment reminder that	Patients receive a pre-commitment prompt
mention asking the provider for a flu vaccine.	asking about their intention to get an influenza
Experimental: Direct appointment scheduling	vaccination
reminder + No pre-appointment reminder +	Behavioral: Portal Reminders for Influenza
No pre-commitment prompt	Vaccination: Direct scheduling link: Patients
Participants receive 1) reminder/recall	receive reminder/recall messages via the
messages regarding influenza vaccination via	patient portal to get an influenza vaccination
the patient portal with a link enabling direct	that include a direct scheduling link, enabling
scheduling, but do not receive a pre-	the patient to directly schedule a flu vaccination
appointment reminder that mention asking	only visit.
the provider for a flu vaccine, or a pre- commitment prompt asking if they plan to receive the influenza vaccine in the upcoming season.	
Experimental: No direct appointment	Behavioral: Portal Reminders for Influenza
scheduling reminder + Pre-appointment	Vaccination: No direct scheduling link: Patients
reminder + Pre-commitment prompt	receive reminder/recall messages via the
Participants receive 1) reminder/recall	patient portal to get an influenza vaccination
messages regarding influenza vaccination via	(no direct scheduling link included).
the patient portal without a link enabling	Behavioral: Pre-Appointment influenza
direct scheduling, 2) a pre-appointment	vaccination reminder: Patients receive modified
reminder that mentions asking the provider	pre-appointment reminders for upcoming
for a flu vaccine, and 3) a pre-commitment	scheduled appointments that include language
prompt asking if they plan to receive the	encouraging patients to ask the provider for the
influenza vaccine in the upcoming season.	flu vaccine.
	Behavioral: Pre-commitment prompt Patients receive a pre-commitment prompt asking about their intention to get an influenza vaccination
Experimental: No direct appointment scheduling reminder + Pre-appointment reminder + No pre-commitment prompt	Behavioral: Portal Reminders for Influenza Vaccination: No direct scheduling link: Patients receive reminder/recall messages via the patient portal to get an influenza vaccination
Participants receive 1) reminder/recall	(no direct scheduling link included).
messages regarding influenza vaccination via	Behavioral: Pre-Appointment influenza
the patient portal without a link enabling	vaccination reminder: Patients receive modified
direct scheduling, and 2 a pre-appointment	pre-appointment reminders for upcoming
reminder that mentions asking the provider	scheduled appointments that include language
for a flu vaccine, but do not receive a pre-	encouraging patients to ask the provider for the
commitment prompt asking if they plan to	flu vaccine.

· · · · · · · · · · · · · · · · · · ·	
receive the influenza vaccine in the upcoming	
season.	
Experimental: No direct appointment	Behavioral: Portal Reminders for Influenza
scheduling reminder + No pre-appointment	Vaccination: No direct scheduling link: Patients
reminder + Pre-commitment prompt	receive reminder/recall messages via the
	patient portal to get an influenza vaccination
Participants receive 1) reminder/recall	(no direct scheduling link included).
messages regarding influenza vaccination via	
the patient portal without a link enabling	Behavioral: Pre-commitment prompt
direct scheduling, and 2)a pre-commitment	Patients receive a pre-commitment prompt
prompt asking if they plan to receive the	asking about their intention to get an influenza
influenza vaccine in the upcoming season,	vaccination
but do not receive a pre-appointment	
reminder that mentions asking the provider	
for a flu vaccine.	
Experimental: No direct appointment	Behavioral: Portal Reminders for Influenza
scheduling reminder + No pre-appointment	Vaccination: No direct scheduling link: Patients
reminder + No Pre-commitment prompt	receive reminder/recall messages via the
	patient portal to get an influenza vaccination
Participants receive 1) reminder/recall	(no direct scheduling link included).
messages regarding influenza vaccination via	
the patient portal without a link enabling	
direct scheduling, but do not a pre-	
appointment reminder that mentions asking	
the provider for a flu vaccine, or a pre-	
commitment prompt asking if they plan to	
receive the influenza vaccine in the upcoming	
season.	

Spacing of R/R messages: The pre-commitment prompt will be sent in September, direct appointment scheduling and no direct appointment scheduling reminders will be sent one time per month until record of vaccine receipt appears in the patient EHR in October, November, and December. The pre-appointment reminders will be sent 2-4 days in advance of scheduled visits.

Languages: messages will be in English.

Health Literacy: We will use plain language <7th grade reading level per Flesch-Kincaid analysis.

**Eligibility**: Our EHR will identify subjects who are eligible for either 1 or 2 influenza vaccinations based on ACIP algorithms (2 are recommended for children <9 years who have not had prior vaccination).

## **Inclusion criteria**

Inclusion criteria will involve-- all UCLA primary care patients over 4 months of age who have made at least 1 visit to the practice within the prior 3 years and who have signed up for MyUCLAhealth (UCLA's portal) and have used the portal at least once within 12 months. Currently this includes 298,112 patients; from these patients, index patients per household will be randomly selected.

a. Active patient: We selected >1 visit in 3y based on our prior studies and the literature to focus the intervention on active patients; practices do not have a good mechanism to inactivate patients.

b. Focusing on Portal Users: We can only send portal R/R messages to patients who have signed up for the portal. Since some patients sign up for the portal but never use it we will restrict our inclusion criteria to patients who used the portal within 12m (75% of UCLA patients). This standard has been applied before. We will assess intervention effects for the included population, and also for the entire practice, since the impact of the intervention reflects the extent of portal penetration.

### **Exclusion criteria**

Patients will be excluded if they are not a patient at one of the 67 primary care practices within UCLA's Health System, and/or if they do not meet the above specified requirements for being an active patient or portal user.

# **Main Outcomes and Measures**

Primary Measure: Receipt of >1 influenza vaccine among index patients between 10/1/2020-03/31/2021 as documented in the EHR which is supplemented electronically by the health system with influenza vaccination data from external sources (e.g., pharmacies) and claims data.

Secondary Measures: Receipt of annual influenza vaccine between 10/1/2020-03/31/2021 among all included patients in identified households.

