Study Title: Patient Portal Reminder/Recall for Influenza Vaccination in a Health System- RCT 3
Initial IRB Approval: 12/20/2017
RCT 3 IRB Approval: 8/14/2020
Clinical Trials Registration: NCT04533685

Statistical Analysis

Primary Analysis

We hypothesize that patients receiving pre-commitment prompts will have higher vaccination rates than control arm patients; patients sent pre-appointment reminders will have higher vaccination rates than control arm patients; and patients linked to direct scheduling will have higher vaccination rates than control arm patients. Primary outcomes (patient receipt of flu vaccine) are binary; our main explanatory variable will be an indicator for the receipt of any portal-based R/R or prompt.

The analysis will be based on a 2x2x2 nested factorial design, nested in a parallel 2-arm trial RCT, comparing the effectiveness of combining portal R/R with patient direct appointment scheduling vs. portal R/R alone vs. control (no intervention) on influenza vaccination rates. Both treatment groups will be additionally randomized into 4 groups to receive 1) a R/R message only (with or without direct appointment scheduling link), 2) the R/R message and a pre-commitment prompt, 3) the R/R message and pre-appointment reminder or 4) the R/R message, a pre-commitment prompt, and a pre-appointment flu vaccine reminder.

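### The pre-commitment prompt goes out in September, but both outcome measures count doses only from 1 October, so vaccinations in the first weeks after the prompt are left out of every contrast that involves it

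*Protocol*

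**What the plan says.** Timing of the messages (Protocol, Methods and Procedures, spacing of messages): "The pre-commitment prompt will be sent in September". The general reminders, with or without a scheduling link, go out "one time per month until record of vaccine receipt appears in the patient EHR in October, November, and December". For the third factor, "The pre-appointment reminders will be sent 2-4 days in advance of scheduled visits", with no start month.

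Content of the prompt (Protocol, study arm table): patients get "a pre-commitment prompt asking if they plan to receive the influenza vaccine in the upcoming season".

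Outcomes (Protocol, Main Outcomes and Measures): the primary measure is "Receipt of >1 influenza vaccine among index patients between 10/1/2020-03/31/2021 as documented in the EHR", read here as at least one dose. The secondary measure is "Receipt of annual influenza vaccine between 10/1/2020-03/31/2021 among all included patients in identified households".

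Analysis (SAP, Primary Analysis): "We hypothesize that patients receiving pre-commitment prompts will have higher vaccination rates than control arm patients". The SAP also says that "our main explanatory variable will be an indicator for the receipt of any portal-based R/R or prompt". The model is intent-to-treat and reports risk ratios. It has a prompt term, but prompt against no prompt among patients who get reminders is listed under Secondary Analysis. The SAP gives no outcome dates.

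**The concern.** For the prompt, outcome counting starts after delivery. A patient prompted in September who is vaccinated that month, and has no dose from 1 October on, is counted as a failure. The quickest responses to the prompt are the ones left out.

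Neither document sets a rule that counts, excludes or tests September doses. Two sentences come near. The eligibility sentence has the record system identify patients due one or two doses, but gives no assessment date. The SAP's analysis with self-reported vaccination adds a data source, not a month.

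At stake is what the prompt result means. The prompt asks about the season and the hypothesis concerns vaccination rates, but the counted result covers October to March only. The reported measures would not show how much was lost.

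**Working it through.** The documents state no vaccination rate, effect size or power figure, so there is no planned figure to reproduce. The dates come from the protocol; every rate below is assumed.

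**Notation.** Let p be comparator uptake from the first prompt send to 3/31/2021, and s the part of p before 1 October. Let d be the gain over that whole period, and e the September excess due to the prompt (new doses plus doses moved forward). Assume that a September recipient has no later counted dose. This is not quite true of children under 9 who are due two doses, so the loss is slightly smaller for them.

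**Identity.**
- Counted uptake is p − s in the comparator and p + d − s − e with the prompt.
- Counted RD = d − e, against d season-long.
- Counted RR = 1 + (d − e)/(p − s), against 1 + d/p season-long.
- The two RRs agree when e/s = d/p. The counted RR is too low when e > d·s/p and too high when e is smaller.
- Patients needed for the same power, 1 October window relative to full window = [v1/(d − e)²]/[v0/d²]. Here v1 and v0 are the sums of the two binomial variances in the respective windows (unadjusted, equal arms).

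**Isolated contrast, prompt against no prompt.** Assume p = 45%, d = 1 point and s = 5 / 10 / 15%. The season RR is 0.46/0.45 = 1.0222. Break-even e is d·s/p = 0.11 / 0.22 / 0.33 points.

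| e (points) | counted RD (points) | counted RR, s = 5 / 10 / 15% | patient ratio |
|---|---|---|---|
| 0 | 1.00 | 1.0250 / 1.0286 / 1.0333 | 0.97 / 0.92 / 0.85 |
| 0.1 | 0.90 | 1.0225 / 1.0257 / 1.0300 | 1.20 / 1.14 / 1.05 |
| 0.25 | 0.75 | 1.0188 / 1.0214 / 1.0250 | 1.73 / 1.64 / 1.52 |
| 0.5 | 0.50 | 1.0125 / 1.0143 / 1.0167 | 3.88 / 3.68 / 3.40 |
| 1.0 | 0 | 1.0000 | no effect left |

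The RR can be inflated while power is lost: at e = 0.25 and s = 15% the RR is 1.0250, above 1.0222, yet 1.52 times the patients are needed.

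**Stated hypothesis, prompted arms against control.** Every prompted arm also gets general reminders. Add an assumed 2-point reminder gain that falls wholly after 1 October, so d = 3 points. Take p = 45%, s = 10% and e = 0.25.
- RD = 3.0 − 0.25 = 2.75 points.
- Counted RR = 0.3775/0.35 = 1.079; season RR = 0.48/0.45 = 1.067.
- v1 = 0.35·0.65 + 0.3775·0.6225 = 0.4625; v0 = 0.45·0.55 + 0.48·0.52 = 0.4971.
- Patient ratio = (0.4625/0.0275²)/(0.4971/0.03²) = 1.11.
- Break-even e = 3 × 10/45 = 0.67 points.

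**Pooled contrast, any message against control.** The counted RD loses e times the prompted share. Four of the eight message arms are prompted. That is half the patients only if allocation is equal, which is not stated; e = 0.25 would then cost 0.125 points.

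**The case against.** The strongest reply is that one fixed calendar window applied to all nine arms is a valid randomised comparison of October to March receipt. Neither document defines a season-long estimand, and the reference to the upcoming season is the wording of a question to patients. This stands as far as validity goes. It does not show that the window suits a factor delivered before it opens.

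A second reply is that the stated hypothesis compares prompted patients with control. Their gain includes reminders, which start in October if the named months are the sending months, so only the prompt's part can fall in September. This also stands. The patient ratios of 1.52 to 1.73 (e = 0.25) and 3.40 to 3.88 (e = 0.5) belong to the isolated contrast and should not be read as the trial's overall loss of power.

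A third reply is that an earlier start dilutes the risk ratios of October-start factors. That is true, and is costed under the fix.

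A reader might also see a contradiction in the reminder schedule, over whether a September dose stops the reminders. The sentence is ambiguous on this, and no contradiction can be drawn from it.

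**Conclusion.** The date mismatch is certain and nothing else in the documents cures it. Counted risk differences for contrasts involving prompted arms lose the September excess, in full or in proportion to the prompted share. The risk ratio matches the season-long one only when September uptake rises in the same proportion as season uptake.

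The size cannot be settled from the documents. It is small if the prompt goes out late in September: with e = 0.1 and s = 5%, the isolated RR is 1.0225 against 1.0222. It can be material for the isolated contrast with an earlier send, and is smaller against control.

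A reader might infer that the window always weakens the prompt's risk ratio, or that it will hide or reverse the effect. The documents support neither. The ratio can rise as well as fall. Hiding needs e equal to the contrast's whole gain (1 point isolated or 3 points against control, in the examples), and reversal needs more. No figure in the documents points to either.

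This should be fixed: a primary hypothesis and a primary model term are affected, and the change is cheap.

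**What to change.** In both outcome measures, start the window for all nine arms on one common calendar date, no later than the first prompt send. Use an earlier date if randomisation or the first pre-appointment reminder comes first, and state when those reminders begin. Keep the 3/31/2021 end and put the same window in the SAP. Exclude no one because of doses recorded after randomisation. Keep the 1 October window as a prespecified sensitivity analysis.

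If the sponsor keeps 1 October as primary, the minimum is a prespecified analysis that includes September for every contrast involving the prompt.

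The cost is two start dates, one SAP sentence and about one more month of extraction, assuming that the record, external and claims sources cover September. For October-start factors the risk difference is unchanged, but the RR excess over 1 falls by s/p: 5/45, 10/45 and 15/45, or 11 / 22 / 33% under the assumed rates. A 1-point effect then moves from RR 1.025 / 1.029 / 1.033 to 1.022 and needs 1.03 / 1.08 / 1.17 times the patients. The sensitivity analysis keeps the undiluted ratio available. The messaging schedule does not change.

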We will employ intent-to-treat analyses using mixed effects log-binomial regression models with practice random effects, an approach recommended for RCTs in which the goal is to estimate the causal effects of interventions on individuals, adjusted for clustering of patients by practice. The primary model terms will be general reminder arm (general reminder v. no general reminder), and interactions between general reminder arm and (1) pre-commitment arm (pre-commitment question v. no pre-commitment question), (2) pre-appointment reminder arm (pre-appointment reminder v. no pre-appointment reminder) and (3) direct scheduling arm (general reminder links v. does not link to direct scheduling).). Models will adjust for the following patient characteristics: age, gender, race/ethnicity, primary language, primary insurer, and prior receipt of influenza vaccines in the last two years. Evaluation of study hypotheses will be performed using model contrasts, and treatment effects will be reported in terms of risk ratios and 95% CIs. In the event of computational issues, we will replace the log-binomial specification with a log-Poisson specification, and use model-robust standard errors for inference on treatment effect risk ratios.

Secondary Analysis

Secondary analyses will include evaluation of process measures (e.g., missed opportunities); evaluation of effect modification by patient characteristics; comparison of receiving precommitment intervention and pre-appointment reminder intervention with not receiving those interventions, however still receiving reminder letters; and evaluation of vaccination receipt including self-reported vaccinations. Process measures will be analyzed similarly to the primary outcome, but using different distributions and link functions as appropriate (e.g., negative binomial distributions for number of missed opportunities). Effect heterogeneity will be evaluated by introducing interaction terms into the primary model specification. All secondary analyses will use a significance level of 0.05. All analyses will be performed using SAS v. 9.4 (SAS Institute Inc., Cary, NC).

Process measures: We assessed the percentage of patients who opened the portal reminder letter, as well as the source of influenza vaccination data (health system within UCLA practices, external source via data transfer, patient/proxy update through normal portal processes, or patient/proxy update in response to portal reminders.

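### If transfer and claims miss some outside doses, vaccinations moved to UCLA could register as gains in the direct-scheduling contrast and, less so, the pre-appointment contrast; the SAP does not separate the two

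*Protocol*

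**What the plan says.** The Protocol (Main Outcomes and Measures) defines the primary measure as receipt of "influenza vaccine among index patients between 10/1/2020-03/31/2021", as documented in an EHR that is "supplemented electronically by the health system with influenza vaccination data from external sources (e.g., pharmacies) and claims data". Neither document says how complete that supplementation is.

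The study arm table (Protocol, Methods and Procedures) describes the two components at issue. Link messages "include a direct scheduling link, enabling the patient to directly schedule a flu vaccination only visit". The other component consists of modified "pre-appointment reminders for upcoming scheduled appointments that include language encouraging patients to ask the provider for the flu vaccine". The booking site is not named; a portal link and this system's own appointments imply UCLA.

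The SAP's Process measures paragraph lists the "source of influenza vaccination data (health system within UCLA practices, external source via data transfer, patient/proxy update through normal portal processes" and, as a fourth route, "patient/proxy update in response to portal reminders"). Its Secondary Analysis section says that process measures will be analysed in much the same way as the primary outcome, with other distributions and links where needed. It also plans an evaluation of vaccination that includes self-reported doses. Treatment effects in the primary model are risk ratios with 95% CIs.

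**The concern.** The hypotheses are about vaccination rates, but the measured outcome is a recorded dose. The two differ when the chance of being recorded depends on where the dose was given. Two randomised components act through visits in the health system. A patient who would have used a pharmacy, and who is vaccinated at UCLA instead because of the link, goes from recorded with probability c to recorded directly. Nothing has changed for that patient except the venue.

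Randomisation does not protect against this, because venue is altered after randomisation by the component itself. Practice random effects and baseline covariates do not remove it either. The bias runs one way, toward benefit.

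The self-report analysis has a purpose only if the electronic feeds miss some doses, so the plan itself suggests that c may be below 1. With a large sample, a small artefact could be read as an effect of the link.

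**Working it through.** The documents give no sample size, expected rate, allocation ratio or capture completeness, so there is no planned figure to reproduce. Every numerical input below is an assumption, chosen to show a range.

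**Identity.** Let U and E be the shares of all patients vaccinated at UCLA and outside in the comparator, s the share moved from outside to UCLA, and c the captured fraction of outside doses. UCLA doses are taken as fully recorded and true vaccination as unchanged.

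- Recorded rate, comparator: U + cE
- Recorded rate, component: (U + s) + c(E - s)
- Difference: s(1 - c)

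**First set of assumptions.** U = 30%, E = 20%, 150,000 index patients, nine equal arms. Link v. no link then has 4 × 150,000 / 9 = 66,667 per side. With comparator recorded rate p, SE(log RR) = sqrt[((1-p)/p) × 2/66,667], ignoring clustering.

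| s (points) | c | Recorded rates | False gain (points) | False RR | Expected z |
|---|---|---|---|---|---|
| 2 | 0.60 | 42.0% to 42.8% | 0.8 | 1.019 | 2.93 |
| 2 | 0.75 | 45.0% to 45.5% | 0.5 | 1.011 | 1.82 |
| 2 | 0.90 | 48.0% to 48.2% | 0.2 | 1.004 | 0.73 |
| 3 | 0.60 | 42.0% to 43.2% | 1.2 | 1.029 | 4.38 |
| 3 | 0.75 | 45.0% to 45.75% | 0.75 | 1.017 | 2.73 |
| 3 | 0.90 | 48.0% to 48.3% | 0.3 | 1.006 | 1.09 |

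For the fifth row: SE = sqrt[(0.55/0.45) × 2/66,667] = 0.00606, log(0.4575/0.45) = 0.01653, and z = 0.01653/0.00606 = 2.73. Moving 3 points out of 20 means that 3/20 = 15% of outside-vaccinated patients change venue because of the link.

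**Second set of assumptions.** True uptake 60% in both groups, 40% of doses given outside, and 18,632 per group (298,112/16, purely illustrative, since 298,112 is the pool before index patients are selected). The last two columns give the chance of a significant result favouring the component at two-sided 0.05, where 2.5% is nominal.

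| c | s (points) | False gain (points) | False RR | 18,632 per group | 5,000 per group |
|---|---|---|---|---|---|
| 1.00 | any | 0 | 1.000 | 2.5% | 2.5% |
| 0.90 | 2 | 0.2 | 1.003 | 5.8% | 3.9% |
| 0.90 | 5 | 0.5 | 1.009 | 16% | 7.3% |
| 0.80 | 5 | 1.0 | 1.018 | 49% | 17% |

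Across uptake 50-70%, outside share 30-40%, c 0.60-0.95 and s 1-5 points, the false RR runs from 1.001 to 1.048.

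**Can source data separate the two?** Take s = 3 points and true c = 0.75. UCLA doses rise by 3 points and transferred doses fall by 0.75 × 3 = 2.25 points, so the recorded effect is 3 - 2.25 = +0.75. Dividing the transferred change by c gives 3 - 2.25/0.75 = 0, the true effect. If c is set at 0.90, the estimate is 3 - 2.5 = +0.5; at 0.60 it is 3 - 3.75 = -0.75. The grid therefore gives a range, not a point correction, but the offsetting pattern by source is visible whatever c is.

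**The case against.** Four points on the other side carry weight.

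- **Relocation as such is not a gain.** A reader might infer that any move to UCLA counts as added vaccination. It does so only for doses that both the external feeds and claims would have missed. The primary outcome is explicitly supplemented from both.
- **Source is not left wholly descriptive.** A reader might infer that the SAP plans no comparison of source by arm. The documents do not support that: source is listed under process measures, and these are to be analysed like the primary outcome. What is missing is narrower. There is no commitment to source-specific contrasts for these two components, and no statement of how they would bear on the primary result.
- **The self-report analysis is a partial safeguard.** It can recover outside doses that transfer missed. Within the reminder arms both sides receive reminders, so both have the self-update route. Against the no-message control it is not even-handed, because updates prompted by a portal reminder cannot arise there.
- **The pre-appointment reminder is a weaker route.** It reaches only patients who already have a visit booked, so it can relocate fewer people than the link.

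It is also fair to say that the magnitudes are wholly assumed. The larger z values need appreciable venue switching and poor capture; at c = 0.90 and s = 3 points, z is 1.09.

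All of this limits the size and reach of the concern. None of it supplies a way to tell relocation from added vaccination in the primary contrasts.

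**Conclusion.** The concern holds as a conditional bias. To the extent that outside doses are not captured, relocation to UCLA could add s(1-c) to the recorded effect of direct scheduling and, to a lesser degree, of the pre-appointment reminder. Under the assumptions above, that is from 0.2 points (s = 2, c = 0.90) to 1.2 points (s = 3, c = 0.60), and it is zero if c = 1 or s = 0. The documents cannot place the trial within that range. The conclusion rests on UCLA doses being fully recorded and on the link booking visits at UCLA, both of which are inferred.

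A reader might go further and take a positive link effect to be an artefact. The documents do not support that: with high capture or little switching the bias is negligible. The defensible conclusion is that, as written, the plan would not let a reader tell a small true effect from better recording. That merits a change to the SAP but does not undermine the design.

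**What to change.** Keep the primary outcome and amend the SAP as follows.

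1. Compare UCLA-administered doses and externally transferred doses separately by randomised arm, by intent to treat, for the direct-scheduling and pre-appointment contrasts. Report these as risk differences standardised from the primary model, because risk ratios by source cannot be added together.
2. Report the sensitivity estimate, change in UCLA doses + (change in transferred doses)/c, for c from 0.6 to 1.0. State the assumption that c is equal across arms. At c = 1.0 this is the recorded effect on UCLA and transferred doses combined.
3. State in advance that a rise in UCLA doses offset by a fall in outside doses will be read as relocation, not as increased vaccination.
4. Cite the planned self-report analysis as supporting evidence for contrasts within the reminder arms only, and say explicitly whether reminder-prompted self-updates are excluded from the primary outcome. Their place in a secondary analysis implies exclusion but does not state it.

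Repeating the contrasts in patients whose insurer supplies claims should be added only if those insurers can be identified at baseline; the documents do not say which they are.

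The cost is some SAP wording and a few more model runs with a standardisation step, on source data that the plan already collects. The sensitivity estimate may be slightly less favourable than the recorded one.
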